#### **7.1.2.10 Guidance for Treatment of adverse event**

When a subject shows an adverse event, the investigators should always consider the necessity of treatment of adverse events as soon as possible regardless of the relationship to study drugs. The investigators should carefully monitor all testing results including those that are not usually done in the routine medical examination in the sites and treat the adverse events as soon as possible before they have an effect on subjects or lead to study discontinuations. Considering the safety profile of the study drugs, the following treatment may be considered but not limited to these adverse events or treatments. It is always important to consider the treatment of adverse events first.

- Pyrexia

Most of these adverse events reported in previous clinical studies were mild to moderate and reversible. Pyrexia is one of the major signs of infection, and it is important to identify the cause of pyrexia. Thus, if pyrexia is not related to target infection of the study, any clinical testing and assessment need to be attempted to identify the cause of pyrexia such as bacterial infection. Antibacterials, antipyretics or any other appropriate treatment should be considered based on the clinical testing.

- Gastrointestinal events (nausea, vomiting, abdominal pain or diarrhea)

Most of these adverse events reported in previous clinical studies were mild to moderate and reversible. Appropriate antiemetic or antiflatulent treatment should be considered.

- Hepatic events (including asymptomatic elevations in transaminases and/or bilirubin)

Most of hepatic adverse events reported in previous clinical studies were mild to moderate and reversible. Interruption of suspicious concomitant drugs and/or adding hepatic function improving drugs should be considered.

- Visual disturbance

Most of these adverse events reported in previous clinical studies were mild to moderate and reversible without treatment.

If adverse events relate to study medication and they become a major issue in spite of the above attempt, interruption of study drugs should be considered before study drug discontinuation.

### **7.1.2.11 Domiciling**

Hospitalization is required until all procedures other than study drug administration are completed on Day 9 (9 days and 8 nights after the initiation of study drug). At the discretion of the investigator, subjects may be requested to remain in the investigator's site longer.

### **7.1.3 Laboratory Procedures/Assessments**

Details regarding specific laboratory procedures/assessments to be performed in this trial are provided below. Laboratory testing is performed in the local laboratory (or its outsourcing). Laboratory testing is performed at the timing of dosage in scheduled visit. The total amount of blood to be drawn/collected over the course of the trial (from pre-trial to post-trial visits), including approximate blood volumes drawn/collected by visit and by sample type per subject can be found in Section 12.4. If abnormal laboratory findings are observed, its abnormality is appropriately followed up until stabilization or recovery to baseline.

#### **7.1.3.1 Laboratory Safety Evaluations (Hematology, Chemistry and Urinalysis)**

Laboratory tests for hematology, chemistry are specified in [Table 20](#) to [Table 22](#).

Table 20 Laboratory Tests (Hematology)

Red blood cell count (RBC)
Hemoglobin
Hematocrit
Platelet count
White blood cell count (WBC)
WBC differential (neutrophil, eosinophil, basophil, lymphocyte, monocyte)

Table 21 Laboratory Tests (Blood Chemistry)

Total protein	Blood Urea Nitrogen
Albumin	Creatinine
Aspartate aminotransferase (AST)	Uric acid
Alanine aminotransferase (ALT)	CRP
Alkaline phosphatase	Calcium
LDH	Chloride
Total Bilirubin	Potassium
Direct Bilirubin	Sodium
	Magnesium

Table 22 Laboratory Test (Other)

Serum hCG (Total hCG or $\beta$ -hCG): female subjects of childbearing potential
Aspergillus antibody (only for subject with Chronic pulmonary aspergillosis): perform at Screening visit only
Galactomannan antigen (ELISA): perform for the subject with aspergillosis only
$\beta$ -D-Glucan: perform for the subject with aspergillosis only

Serum electrolytes (K, Ca, Mg) must be measured on the same day and recorded in the source document and eCRF, in case an unscheduled 12-lead electrocardiogram is performed. In case adrenal insufficiency is observed, serum electrolytes (K, Ca, Mg) must be measured, evaluated and recorded in the source documents and eCRF.

If CRP is measured at the unscheduled visit, all of these data are recorded in the source document and eCRF appropriately.

Urine pregnancy testing can be conducted for confirmation of subject eligibility and it is not required to record in the eCRF. Even though urine pregnancy testing is conducted, serum pregnancy testing should be conducted as a screening testing and it is recorded in the source document and eCRF appropriately.

### 7.1.3.2 Pharmacokinetic/Pharmacodynamic Evaluations

[figure not shown]
Measurement for PK analysis will be performed in collected samples.

#### 7.1.3.2.1 Blood Collection for Plasma MK-5592

Sample collection, storage and shipment instructions for plasma samples will be provided separately.

### **7.1.3.3 Future Biomedical Research**

CDI

A large black rectangular redaction box covers the majority of the page content below the section header.

[figure not shown]
### **7.1.4 Other Procedures**

#### **7.1.4.1 Withdrawal/Discontinuation**

When a subject discontinues/withdraws prior to trial completion, all applicable activities scheduled for the final trial visit should be performed at the time of discontinuation. Any adverse events which are present at the time of discontinuation/withdrawal should be followed in accordance with the safety requirements outlined in Section 7.2 - Assessing and Recording Adverse Events.

##### **7.1.4.1.1 Withdrawal From Future Biomedical Research**

CDI

A large black rectangular redaction box covers the majority of the page content below the section header.

##### **7.1.4.2 Blinding/Unblinding**

This is an open label trial; there is no blinding for this trial.

### **7.1.5 Visit Requirements**

Visit requirements are outlined in Section 6.0 - Trial Flow Chart. Specific procedure-related details are provided above in Section 7.1 - Trial Procedures.

### **7.1.5.1 Procedure of MK-5592 Treatment for Subjects in case That Zygomycete are Observed During the Treatment Period in Voriconazole Treatment Arm**

Subjects in whom zygomycetes are detected during the treatment period in the voriconazole treatment arm can receive the MK-5592 by investigator's discretion after the discontinuation of voriconazole treatment. MK-5592 dosing can be initiated after performing all observations, testing and evaluations at the end of treatment and the signing of a new informed consent.

## **7.2 Assessing and Recording Adverse Events**

An adverse event is defined as any untoward medical occurrence in a patient or clinical investigation subject administered a pharmaceutical product and which does not necessarily have to have a causal relationship with this treatment. An adverse event can therefore be any unfavourable and unintended sign (including an abnormal laboratory finding, for example), symptom, or disease temporally associated with the use of a medicinal product or protocol-specified procedure, whether or not considered related to the medicinal product or protocol-specified procedure. Any worsening (i.e., any clinically significant adverse change in frequency and/or intensity) of a preexisting condition that is temporally associated with the use of the Sponsor's product, is also an adverse event.

Changes resulting from normal growth and development that do not vary significantly in frequency or severity from expected levels are not to be considered adverse events. Examples of this may include, but are not limited to, teething, typical crying in infants and children and onset of menses or menopause occurring at a physiologically appropriate time.

Sponsor's product includes any pharmaceutical product, biological product, device, diagnostic agent or protocol-specified procedure, whether investigational (including placebo or active comparator medication) or marketed, manufactured by, licensed by, provided by or distributed by the Sponsor for human use.

Adverse events may occur during clinical trials, or as prescribed in clinical practice, from overdose (whether accidental or intentional), from abuse and from withdrawal.

All adverse events that occur after the consent form is signed but before treatment allocation/randomization must be reported by the investigator if they cause the subject to be excluded from the trial, or are the result of a protocol-specified intervention, including but not limited to washout or discontinuation of usual therapy, diet, placebo treatment or a procedure. From the time of treatment allocation/randomization through 14 days following cessation of treatment, all adverse events must be reported by the investigator. Such events will be recorded at each examination on the Adverse Event case report forms/worksheets. The reporting timeframe for adverse events meeting any serious criteria is described in section 7.2.3.1. The investigator will make every attempt to follow all subjects with non-serious adverse events for outcome.

Electronic reporting procedures can be found in the Electronic Data Capture (EDC) data entry guidelines. Paper reporting procedures can be found in the Investigator Trial File Binder (or equivalent).

### **7.2.1 Definition of an Overdose for This Protocol and Reporting of Overdose to the Sponsor**

In this trial, an overdose is any dose higher than the dose below for cohort 2.

MK-5592 solid oral tablet and IV solution: 300 mg/time and 300 mg/day (600 mg/day on Day 1).

Voriconazole IV: 6 mg/kg/time and 12 mg/kg/day on Day 1, 4 mg/kg/time and 8 mg/kg/day after Day 1

Voriconazole oral tablet: 300 mg/time and 600 mg/day on Day 1, 200 mg/time and 400 mg/day after Day 1

In case of higher than the above criteria, overdose is not applicable when the voriconazole dosage is adjusted based on the TDM, however overdose is any higher than 6 mg/kg for IV and 300 mg for oral tablet as a single dose.

In case of higher than the above criteria, overdose is not applicable when the MK-5592 and voriconazole daily dosage is exceeded according to the allowance of dosing interval by Day 5.

If an adverse event(s) is associated with (“results from”) the overdose of Sponsor's product or vaccine, the adverse event(s) is reported as a serious adverse event, even if no other seriousness criteria are met.

If a dose of Sponsor's product or vaccine meeting the protocol definition of overdose is taken without any associated clinical symptoms or abnormal laboratory results, the overdose is reported as a non-serious Event of Clinical Interest (ECI), using the terminology “accidental or intentional overdose without adverse effect.”

All reports of overdose with and without an adverse event must be reported within 24 hours to the Sponsor either by electronic media or paper. Sponsor Contact information can be found in the Investigator Trial File Binder.

### **7.2.2 Reporting of Pregnancy and Lactation to the Sponsor**

Although pregnancy and lactation are not considered adverse events, it is the responsibility of investigators or their designees to report any pregnancy or lactation in a subject (spontaneously reported to them) that occurs during the trial or within 14 days of completing the trial. All subjects who become pregnant must be followed to the completion/termination of the pregnancy. Pregnancy outcomes of spontaneous abortion, missed abortion, benign hydatidiform mole, blighted ovum, fetal death, intrauterine death, miscarriage and stillbirth

must be reported as serious events (Important Medical Events). If the pregnancy continues to term, the outcome (health of infant) must also be reported.

Such events must be reported within 24 hours to the Sponsor either by electronic media or paper. Sponsor Contact information can be found in the Investigator Trial File Binder.

### **7.2.3 Immediate Reporting of Adverse Events to the Sponsor**

#### **7.2.3.1 Serious Adverse Events**

A serious adverse event is any adverse event occurring at any dose or during any use of Sponsor's product that:

- Results in death;
- Is life threatening;
- Results in persistent or significant disability/incapacity;
- Results in or prolongs an existing inpatient hospitalization;
- Is a congenital anomaly/birth defect;
- Is an other important medical event.

**Note:** In addition to the above criteria, adverse events meeting either of the below criteria, although not serious per ICH definition, are reportable to the Sponsor in the same timeframe as SAEs to meet certain local requirements. Therefore, these events are considered serious by the Sponsor for collection purposes.

- Is a cancer;
- Is associated with an overdose.

Refer to [Table 23](#) for additional details regarding each of the above criteria.

For the time period beginning when the consent form is signed until treatment allocation/randomization, any serious adverse event, or follow up to a serious adverse event, including death due to any cause, that occurs to any subject must be reported within 24 hours to the Sponsor if it causes the subject to be excluded from the trial, or is the result of a protocol-specified intervention, including but not limited to washout or discontinuation of usual therapy, diet, placebo treatment or a procedure.

For the time period beginning at treatment allocation/randomization through 14 days following cessation of treatment, any serious adverse event, or follow up to a serious adverse event, including death due to any cause, whether or not related to the Sponsor's product, must be reported within 24 hours to the Sponsor either by electronic media or paper. Electronic reporting procedures can be found in the EDC data entry guidelines. Paper reporting procedures can be found in the Investigator Trial File Binder (or equivalent).

Additionally, any serious adverse event, considered by an investigator who is a qualified physician to be related to the Sponsor's product that is brought to the attention of the

investigator at any time outside of the time period specified in the previous paragraph also must be reported immediately to the Sponsor.

All subjects with serious adverse events must be followed up for outcome.

### **7.2.3.2 Events of Clinical Interest**

Selected non-serious and serious adverse events are also known as Events of Clinical Interest (ECI) and must be recorded as such on the Adverse Event case report forms/worksheets and reported within 24 hours to the Sponsor either by electronic media or paper. Sponsor Contact information can be found in the Investigator Trial File Binder.

Events of clinical interest for this trial include:

- a. an overdose of Sponsor's product, as defined in Section 7.2.1 - Definition of an Overdose for This Protocol and Reporting of Overdose to the Sponsor, that is not associated with clinical symptoms or abnormal laboratory results.
- b. an elevated AST or ALT lab value that is greater than or equal to 3X the upper limit of normal and an elevated total bilirubin lab value that is greater than or equal to 2X the upper limit of normal and, at the same time, an alkaline phosphatase lab value that is less than 2X the upper limit of normal, as determined by way of protocol-specified laboratory testing or unscheduled laboratory testing.\*

**\*Note:** These criteria are based upon available regulatory guidance documents. The purpose of the criteria is to specify a threshold of abnormal hepatic tests that may require an additional evaluation for an underlying etiology. The trial site guidance for assessment and follow up of these criteria can be found in the Investigator Trial File Binder.

### **7.2.4 Evaluating Adverse Events**

An investigator who is a qualified physician will evaluate all adverse events according to the NCI Common Terminology for Adverse Events (CTCAE), version 4.0. Any adverse event which changes CTCAE grade over the course of a given episode will have each change of grade recorded on the adverse event case report forms/worksheets.

All adverse events regardless of CTCAE grade must also be evaluated for seriousness.

**Table 23 Evaluating Adverse Events**

An investigator who is a qualified physician, will evaluate all adverse events as to:

V4.0 CTCAE Grading	Grade 1	Mild; asymptomatic or mild symptoms; clinical or diagnostic observations only; intervention not indicated.
	Grade 2	Moderate; minimal, local or noninvasive intervention indicated; limiting age-appropriate instrumental ADL.
	Grade 3	Severe or medically significant but not immediately life-threatening; hospitalization or prolongation or hospitalization indicated; disabling; limiting self-care ADL.
	Grade 4	Life threatening consequences; urgent intervention indicated.
	Grade 5	Death related to AE
Seriousness	A serious adverse event is any adverse event occurring at any dose or during any use of Sponsor's product that:	
	† Results in death; or	
	† Is life threatening; or places the subject, in the view of the investigator, at immediate risk of death from the event as it occurred (Note: This does not include an adverse event that, had it occurred in a more severe form, might have caused death.); or	
	† Results in a persistent or significant disability/incapacity (substantial disruption of one's ability to conduct normal life functions); or	
	† Results in or prolongs an existing inpatient hospitalization (hospitalization is defined as an inpatient admission, regardless of length of stay, even if the hospitalization is a precautionary measure for continued observation. (Note: Hospitalization [including hospitalization for an elective procedure] for a preexisting condition which has not worsened does not constitute a serious adverse event.); or	
	† Is a congenital anomaly/birth defect (in offspring of subject taking the product regardless of time to diagnosis); or	
	Is a new cancer; (that is not a condition of the study) or	
	Is an overdose (whether accidental or intentional). Any adverse event associated with an overdose is considered a serious adverse event. An overdose that is not associated with an adverse event is considered a non-serious event of clinical interest and must be reported within 24 hours.	
	Other important medical events that may not result in death, not be life threatening, or not require hospitalization may be considered a serious adverse event when, based upon appropriate medical judgment, the event may jeopardize the subject and may require medical or surgical intervention to prevent one of the outcomes listed previously (designated above by a †).	
Duration	Record the start and stop dates of the adverse event. If less than 1 day, indicate the appropriate length of time and units	
Action taken	Did the adverse event cause the Sponsor's product to be discontinued?	
Relationship to test drug	Did the Sponsor's product cause the adverse event? The determination of the likelihood that the Sponsor's product caused the adverse event will be provided by an investigator who is a qualified physician. The investigator's signed/dated initials on the source document or worksheet that supports the causality noted on the AE form, ensures that a medically qualified assessment of causality was done. This initialed document must be retained for the required regulatory time frame. The criteria below are intended as reference guidelines to assist the investigator in assessing the likelihood of a relationship between the test drug and the adverse event based upon the available information.	
	The following components are to be used to assess the relationship between the Sponsor's product and the AE; the greater the correlation with the components and their respective elements (in number and/or intensity), the more likely the Sponsor's product caused the adverse event (AE):	
Exposure	Is there evidence that the subject was actually exposed to the Sponsor's product such as: reliable history, acceptable compliance assessment (pill count, diary, etc.), expected pharmacologic effect, or measurement of drug/metabolite in bodily specimen?	
Time Course	Did the AE follow in a reasonable temporal sequence from administration of the Sponsor's product? Is the time of onset of the AE compatible with a drug-induced effect (applies to trials with investigational medicinal product)?	
Likely Cause	Is the AE not reasonably explained by another etiology such as underlying disease, other drug(s)/vaccine(s), or other host or environmental factors	

Relationship to Sponsor's Product (continued)	The following components are to be used to assess the relationship between the test drug and the AE: (continued)	
	Dechallenge	Was the Sponsor's product discontinued or dose/exposure/frequency reduced? If yes, did the AE resolve or improve? If yes, this is a positive dechallenge. If no, this is a negative dechallenge. (Note: This criterion is not applicable if: (1) the AE resulted in death or permanent disability; (2) the AE resolved/improved despite continuation of the Sponsor's product; or (3) the trial is a single-dose drug trial); or (4) Sponsor's product(s) is/are only used one time.)
	Rechallenge	Was the subject re-exposed to the Sponsor's product in this study? If yes, did the AE recur or worsen? If yes, this is a positive rechallenge. If no, this is a negative rechallenge. (Note: This criterion is not applicable if: (1) the initial AE resulted in death or permanent disability, or (2) the trial is a single-dose drug trial); or (3) Sponsor's product(s) is/are used only one time). NOTE: IF A RECHALLENGE IS PLANNED FOR AN ADVERSE EVENT WHICH WAS SERIOUS AND WHICH MAY HAVE BEEN CAUSED BY THE SPONSOR'S PRODUCT, OR IF REEXPOSURE TO THE SPONSOR'S PRODUCT POSES ADDITIONAL POTENTIAL SIGNIFICANT RISK TO THE SUBJECT, THEN THE RECHALLENGE MUST BE APPROVED IN ADVANCE BY THE U.S. CLINICAL MONITOR AS PER DOSE MODIFICATION GUIDELINES IN THE PROTOCOL.
	Consistency with Trial Treatment Profile	Is the clinical/pathological presentation of the AE consistent with previous knowledge regarding the Sponsor's product or drug class pharmacology or toxicology?
The assessment of relationship will be reported on the case report forms /worksheets by an investigator who is a qualified physician according to his/her best clinical judgment, including consideration of the above elements.		
Record one of the following	Use the following scale of criteria as guidance (not all criteria must be present to be indicative of a Sponsor's product relationship).	
Yes, there is a reasonable possibility of Sponsor's product relationship.	There is evidence of exposure to the Sponsor's product. The temporal sequence of the AE onset relative to the administration of the Sponsor's product is reasonable. The AE is more likely explained by the Sponsor's product than by another cause.	
No, there is not a reasonable possibility of Sponsor's product relationship	Subject did not receive the Sponsor's product OR temporal sequence of the AE onset relative to administration of the Sponsor's product is not reasonable OR there is another obvious cause of the AE. (Also entered for a subject with overdose without an associated AE.)	

### **7.2.5 Sponsor Responsibility for Reporting Adverse Events**

All Adverse Events will be reported to regulatory authorities, IRB/IECs and investigators in accordance with all applicable global laws and regulations.

## **7.3 TRIAL GOVERNANCE AND OVERSIGHT**

### **7.3.1 Clinical Adjudication Committee**

A Clinical Adjudication Committee (CAC) will evaluate the following events for the purposes of confirming them according to the criteria in Section 8.0 – Statistical Analysis Plan.

- 1) Diagnosis of deep-seated fungal infection [For subjects with all queries closed, validity of deep-seated fungal infection diagnosed by investigators is assessed]
- 2) Overall Response [For subjects with all queries closed, validity of Overall Response assessed by investigator is assessed (Overall Response, Clinical Response, Radiological Response, Mycological Response)]

All personnel involved in the adjudication process will remain blinded to treatment allocation throughout the trial. Specific details regarding endpoint definitions can be found in the Adjudication Charter.

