- 1) The subject has attributable chronic signs and symptoms [e.g. cough, sputum (bloody sputum or hemoptysis etc), dyspnea, pyrexia, weight decrease etc]
- 2) The subject has a shadow [enhancement of cavity, thickness of cavity wall (enhancement of cavity consolidation), fungus ball-like shadow, progression of pleural thickening or niveau etc.] by chest imaging (CT) and it is judged that other causes are negative.

(c) Mycological criteria: the subject meets one of following criteria by mycological testing or serological testing

- 1) Fungal element of Aspergillus species is detected by direct microscopy in biopsy specimen (bronchial mucosa or lung etc.), BAL, sputum, sputum with transtracheal aspiration, pleural effusion or a sample obtained within 14 days prior to Day 1 using any other appropriate method, or recovery of Aspergillus species by culture of samples obtained within 14 days prior to Day 1 (Proven case)
- 2) Aspergillus species is detected by histopathological testing of samples obtained within 14 days prior to Day 1 (Proven case)
- 3) Galactomannan antigen is detected in serum or bronchoalveolar lavage (BAL) fluid [a positive test result defined as a cut-off index  $\geq 1.0$  (single result from serum or BAL) or  $\geq 0.5$  (2 consecutive results from serum samples)], or aspergillus antibody is detected in serum or BAL (Probable case) Aspergillus antibody within 28 days before the initiation of study therapy, it can be used as a screening result.

- (3) Zygomycosis (The subject is assigned to the MK-5592 treatment arm); Fungal infection is strongly suspected based on clinical symptom and/or characteristic imaging findings and meets at least one of the following criteria: If data of (a) and (b) comes from within 14 days before initiation of study therapy, it can be used as a screening result.
  - (a) Fungal elements of *Zygomycota* spp (*Rhizopus*, *Absidia*, *Rhizomucor*, *Mucor*, *Cunninghamella*, etc.) mold in biopsy sample (bronchial mucosa, lung etc.), broncho-aleveolar lavage fluid, sputum, sputum with transtracheal aspiration, pleural effusion, blood and any other appropriate sample by direct microscopy or *Zygomycota* spp. are observed by culture test.
  - (b) *Zygomycota* spp. is detected by histopathologic test.

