### **8.2.1 Responsibility for Analyses/In-House Blinding**

The statistical analysis of the data obtained from this study will be the responsibility of the Clinical Biostatistics department of the SPONSOR.

This trial is being conducted as an open-label study, i.e., patients, investigators, and SPONSOR personnel will be aware of patient treatment assignments after each patient is enrolled and treatment is assigned.

The Clinical Biostatistics department or designee will generate the randomized allocation schedule for study treatment assignment. Randomization will be implemented by registration center.

This trial is being conducted as an open-label study but the diagnosis and overall response will be assessed by CAC in a blinded manner based on data with masked information such as treatment assignment.

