## 8.2.4 Analysis Populations

### 8.2.4.1 Efficacy Analysis Populations

The Full Analysis Set (FAS) population will serve as the primary population for the analysis of efficacy data in this study. The FAS for a given endpoint consists of all randomized subjects in cohort 2 who:

- Diagnosed as target disease (proven or probable) by CAC
- Receive at least one dose of study treatment
- Have a baseline observation for the analysis endpoint

Subjects with possible invasive aspergillosis may also be enrolled into the study with further evaluation of proven or probable invasive aspergillosis, which must be confirmed by 7 days post-randomization to be included in the FAS analysis.

An Intention To Treat (ITT) population is defined as all randomized subjects in cohort 2 who received at least one dose of study treatment, and the analysis of the primary efficacy endpoint will be performed.

A supportive analysis using the Per-Protocol population in cohort 2 will be also performed for the primary efficacy endpoint. The Per-Protocol population excludes patients due to important deviations from the protocol that may substantially affect the results of the primary efficacy endpoint. Potential violations that may result in the exclusion of a patient from the Per-Protocol population include:

- Subjects with cases that affect the results of the primary efficacy endpoint, confirmed by CAC

The final determination on protocol violations, and thereby the composition of the Per-Protocol population, will be made prior to the final lock of the database and will be documented in a separate memo.

Patients will be included in the treatment group to which they are randomized for the analysis of efficacy data using both the FAS, ITT and Per-Protocol populations. Details on the approach to handling missing data are provided in Section 8.2.5.1.4.

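### The CAC diagnosis that decides entry to the primary efficacy set is not separated from the subject's later course, so FAS membership can depend on response

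*Combined protocol and SAP*

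**What the plan says.** Section 8.2.4.1 makes the FAS the primary efficacy population. Its first condition is "Diagnosed as target disease (proven or probable) by CAC", alongside at least one dose and a baseline observation.

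Section 7.3.1 gives the CAC two tasks. For diagnosis: "For subjects with all queries closed, validity of deep-seated fungal infection diagnosed by investigators is assessed". For response: "For subjects with all queries closed, validity of Overall Response assessed by investigator is assessed". Committee and trigger are the same. Section 7.1.2.9 adds that the investigator's overall response is passed to the CAC.

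On masking, Section 7.3.1 says: "All personnel involved in the adjudication process will remain blinded to treatment allocation throughout the trial". Section 8.2.1 says that "the diagnosis and overall response will be assessed by CAC in a blinded manner", with treatment assignment as the named example of what is masked; Section 8.2.3.3 is similar.

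Some time limits exist. The entry criteria in Section 5.1.2 require screening tests within 7 days before Day 1, most specimens within 14 days before Day 1, and the CPA antibody result within 28 days before study therapy. Subjects entered as possible IA need proven or probable disease "which must be confirmed by 7 days post-randomization to be included in the FAS analysis".

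Section 7.3.1 also points to a document that is not among those supplied: "Specific details regarding endpoint definitions can be found in the Adjudication Charter".

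**The concern.** A subject whose queries are all closed will ordinarily have a complete record, including on-treatment CT, mycology and the investigator's response. If the committee asks only then whether the entry diagnosis was valid, a lesion that failed to shrink is a natural reason to doubt it. The CPA criteria leave room for this. The disease must be active, and for the shadow on CT the requirement is that "it is judged that other causes are negative". For lower respiratory tract IA, a footnote asks for efforts to exclude another cause.

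The primary efficacy result is a response rate with its own interval in each arm. Removing failures from the denominator raises that rate even when it happens equally in both arms, so masking to treatment does not prevent it.

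**Working it through.** **1. Which diagnoses are time-bounded for the CAC**

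| Decision | Limit stated in protocol or SAP |
|---|---|
| Possible IA upgraded to proven/probable | Day 7 after randomization (Section 8.2.4.1, Table 25 footnote) |
| Proven/probable IA upheld or overturned | Entry specimens are dated; no data cut for the CAC review |
| CPA upheld or overturned | Entry specimens are dated; no data cut for the CAC review |

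The target is 15 IA subjects among 90 (Section 8.2.7), so about 90 − 15 = 75 are CPA and fall in the last row. Section 7.3.1 refers to criteria in Section 8, but Section 8 contains no diagnostic criteria and no order for the two reviews.

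**2. Inputs for size**

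From Section 8.2.7: 60 subjects on MK-5592, planning response rates of 60% and 80%, 2:1 allocation. From Section 8.2.5.1.1: Clopper-Pearson 95% intervals. The documents give no CAC rejection rate, so every rejection figure below is an assumption.

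**3. The plan's own figure**

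The lower limit is the 2.5% quantile of Beta(x, n − x + 1).
- 36/60: 46.54% (stated 46.5%).
- 48/60: 67.67% (stated 67.7%).

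Both reproduce. They use all 60 subjects, with no allowance for loss from the FAS.

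**4. Effect of rejection on the rate**

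With true rate p, a fraction a of responders rejected and a fraction b of non-responders rejected, the FAS rate is

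p(1 − a) / [p(1 − a) + (1 − p)(1 − b)].

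- a = b = 10%, p = 60%: 0.54 / (0.54 + 0.36) = 60.0%. No bias.
- a = 5%, b = 20%, p = 60%: 0.57 / (0.57 + 0.32) = 64.0%.
- a = 5%, b = 20%, p = 80%: 0.76 / (0.76 + 0.16) = 82.6%.

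Dropping k non-responders and no responders from 36/60:

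| k | Rate | 95% CI |
|---|---|---|
| 0 | 36/60 = 60.0% | 46.5–72.4 |
| 3 | 36/57 = 63.2% | 49.3–75.6 |
| 6 | 36/54 = 66.7% | 52.5–78.9 |
| 10 | 36/50 = 72.0% | 57.5–83.8 |

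**5. By disease**

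The primary rates are for IA at Day 42 and CPA at Day 84, so the split matters. At 2:1, the MK-5592 arm has about 50 CPA and 10 IA subjects. Again dropping non-responders only:
- CPA: 30/50 = 60.0% (45.2–73.6); five dropped gives 30/45 = 66.7% (51.0–80.0).
- IA: 6/10 = 60.0% (26.2–87.8); one dropped gives 6/9 = 66.7% (29.9–92.5).

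**6. Effect on a difference between arms**

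Use the plan's two rates as illustrative arms, both with a = 5% and b = 20%. A true difference of 80.0 − 60.0 = 20.0 points becomes 82.6 − 64.0 = 18.6 points. Equal true rates stay equal. Rejection blind to arm therefore moves the difference much less than the rates themselves.

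**The case against.** The strongest reply is that the CAC checks the validity of a diagnosis made against dated entry criteria, most of them hard. Proven IA rests on tissue or sterile-site culture, and probable IA and CPA each need a mycological or serological finding. A reader might infer that nothing ties the diagnosis to entry data. The documents do not support that, given the dates in Section 5.1.2 and the Day 7 rule. What remains is narrower: the judgement elements are still open, and no text excludes later evidence when they are applied.

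Second, the trigger in Section 7.3.1 says when a subject is reviewed, not what the diagnosis package contains or which step comes first. The masked items in Section 8.2.1 are given by example, and the charter may set a data cut. This stands as a limit on certainty. However, the charter is cited for endpoint definitions, and a rule that decides the primary efficacy population belongs in the protocol and SAP.

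Third, an ITT analysis of the same endpoint needs no CAC diagnosis (Sections 8.2.4.1 and 8.2.5.1.2). It is a real check, but Table 26 gives it as a supportive point estimate without an interval. It also keeps possible IA subjects who were never confirmed, so for IA a gap between FAS and ITT would not isolate the effect.

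Fourth, the primary objective is safety, no hypothesis is set (Section 8.2.2), and the safety set does not use the CAC diagnosis (Section 8.2.4.2). This is correct and limits the consequence to the descriptive efficacy rates.

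**Conclusion.** The concern holds in a bounded form. As written, the protocol and SAP allow membership of the primary efficacy set to depend on the outcome that the set is used to estimate. The exposure lies in CPA and in proven/probable IA, not in the upgrading of possible IA.

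The bias is upward if non-responders are rejected more often than responders, and absent if rejection is unrelated to response. Plausible sizes from 60.0% are 64.0% under the mixed pattern and 66.7% with six non-responders dropped; these are illustrations, not estimates. A reader might infer that failures will be removed, or that the comparison of arms is compromised. The documents show neither: no rejection rate is given, and masking to treatment guards the comparison better than it guards the absolute rates. The safety set and the ITT rates are unaffected.

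The change is worth making because it is cheap and removes the dependence. The gap does not undermine the trial's primary objective.

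**What to change.** In Sections 7.3.1 and 8.2.4.1:

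- Have the CAC record each subject's diagnosis (proven, probable or neither) and lock it before it sees any post-baseline response data for that subject.
- Set the limit by specimen or scan date, not by visit: up to Day 1, or up to Day 7 after randomization for possible IA. Later central species identification of those isolates (Section 7.1.2.6) and earlier comparison imaging that the CAC may request (Section 7.1.2.5) stay admissible.
- Base FAS membership on the locked record.

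In Section 8.2.5.1.2 and Table 26, add Clopper-Pearson intervals to the ITT rates, and report CAC-rejected subjects by arm and response. If the charter already contains such a data cut, state it in the protocol and SAP.

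The cost is a two-step adjudication package and somewhat longer adjudication, with no new visits, readers or procedures. A diagnosis first confirmed by a later specimen would not count; for possible IA, the Day 7 rule already accepts that loss.
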